4.11. Secondary Analyses

All secondary analyses will be performed for the ITT Population, unless specified otherwise.

4.11.1. Change from Baseline in %-predicted FEV₁

The descriptive statistics of %-predicted FEV₁, absolute, and relative change in %-predicted FEV₁ will be summarized for each visit overall and by preceding treatment group in PTC124-GD-021-CF (study 021). The highest FEV₁ assessment at each visit will be included into the analyses.

4.11.2. **Pulmonary Exacerbations**

The descriptive statistics of the 48-week pulmonary exacerbation rates based on different definitions in Section 5.6 will be reported. The number of subjects with $0, \ge 1, \ge 2$, and ≥ 3 pulmonary exacerbations based on different definitions will also be tabulated as well.

Descriptive statistics of the overall duration of pulmonary exacerbations will be reported.

The above analyses will be performed by preceding treatment group in study 021 and overall.

4.11.3. **FVC**

The absolute change in FVC will be analyzed using descriptive statistics for each visit overall and by preceding treatment group in study 021.

^b Patients with a diagnosis of Gilbert's syndrome need not confirm the laboratory parameter and/or stop study drug unless the total bilirubin value exceeds 3.0 x ULN.

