In $\sim 10\%$ of patients with CF, the causative defect in the CFTR gene is a nonsense mutation that truncates CFTR protein production by introducing a premature stop codon into the CFTR messenger ribonucleic acid (mRNA). PTC Therapeutics, Inc., a biopharmaceutical company located in South Plainfield, NJ, USA has discovered and developed ataluren (PTC124®) as a novel, orally bioavailable, small-molecule drug that promotes ribosomal readthrough of mRNA containing a premature stop codon. Through this mechanism of action, ataluren has the potential to overcome the genetic defect in patients for whom a nonsense mutation causes CF. Pharmacologic proof-of-concept has been demonstrated in animal models and Phase 2 clinical trials. A Phase 3, randomized, double-blind, placebo controlled clinical trial (Study 009) of patients >6 years of age with nmCF randomized to receive ataluren 10 mg/kg in the morning, 10 mg/kg mid-day and 20-mg/kg in the evening; or placebo for 48 weeks showed positive trends favoring ataluren vs placebo for both the primary endpoint, relative change in %-predicted forced expiratory volume in 1 second (FEV₁) at Week 48, and the secondary endpoint, pulmonary exacerbation rate over 48 weeks [Kerem 2014]. A subgroup effect in FEV₁ and pulmonary exacerbation rate showing larger differences favoring ataluren was observed in patients who were not receiving chronic inhaled antibiotics, which was driven by chronic inhaled tobramycin. This same study showed that ataluren was well tolerated; safety profiles were generally similar for ataluren and placebo, other than cases of reversible Grade 3-4 creatinine elevations, which were associated with the combination of potentially nephrotoxic antibiotics with ataluren.

These encouraging data led to the conduct of a confirmatory Phase 3, international, multicenter, randomized, double-blind, placebo-controlled, efficacy and safety study (Study PTC124-GD-021-CF). This ongoing Phase 3 study includes a treatment period of 48 weeks and an estimated recruitment period of 14 months at 93 investigational sites worldwide. The first patient in study PTC124-021-CF initiated study drug treatment on 15 August 2014.

All patients who successfully complete the Phase 3 double-blind, placebo-controlled study (PTC124-GD-021-CF) will be eligible for this Phase 3 open-label, extension study (PTC124-GD-021e-CF).

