6.2. Study Drug Treatment

6.2.1. Duration of Treatment

In this study, treatment will comprise continuous daily treatment with ataluren for up to 96 weeks (~2 years). This study may be further extended by amendment until either ataluren

becomes commercially available or the clinical development of ataluren in nmCF is discontinued.

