2. STUDY OVERVIEW

2.1. Study Design

Study 021e is a Phase 3, international, multicenter, open-label, extension study of ataluren in patients with nmCF that have completed participation in the double-blind study PTC124-GD-021-CF (Study 021).

All eligible patients that completed participation in Study 021 will be enrolled into the study. Eligible subjects will receive oral ataluren administered 3 times per day (TID) at respective morning, midday, and evening doses of 10-, 10-, and 20-mg/kg for 96 weeks. The detailed schedule of assessments are displayed in Table 1.

Screening and baseline procedures are structured to avoid a gap in treatment between the double-blind study (PTC124-GD-021-CF) and this extension study. When possible, Screening/Baseline (Visit 1) for this extension study should occur on the same day as the End-of-Study visit for the double-blind study (PTC124-GD-021-CF). During the treatment period, study assessments will be performed at clinic visits at Week 12 and thereafter every 12 weeks until the end of the study.

Planned interim safety analyses will be conducted by an independent data monitoring committee (DMC). The first safety review will occur when ~ 100 patients have completed >=36 weeks of treatment. The second safety review will occur when ~ 100 patients have completed >=72 weeks of treatment.

The study will be terminated prematurely according to company's strategic decision on March 2, 2017. All subject who are on-going by then will be discontinued.

Table 1. Schedule of Events

| Study Period | Screening/B aseline | Treatment Period | | | | | | Post-Treatment | | |
|---|---------------------|------------------|----|----|----|----|----|----------------|-----------------------------|--------------------|
| Study Week (±7 days) | Day 1 | 12 | 24 | 36 | 48 | 60 | 72 | 84 | End of Tx/ Premature D/C 96 | 4 Weeks Post-Tx |
| Visit | 1 | 2 | 3 | 4 | 5 | 6 | 7 | 8 | 9 | 10 |
| Informed consent | X | | | | | | | | | |
| CFQ-R administration | X ^a | X | X | X | X | X | X | X | X | |
| Vital signs | Xa | X | X | X | X | X | X | X | X | X |
| Height | X ^a | X | X | X | X | X | X | X | X | X |
| Weight | X ^a | X | X | X | X | X | X | X | X | X |
| Physical examination | X ^a | | | | X | | | | X | X |
| Hematology | X ^a | X | X | X | X | X | X | X | X | X |
| Biochemistry | X ^a | X | X | X | X | X | X | X | X | X |
| Urinalysis | Xa | X | X | X | X | X | X | X | X | X |
| Renal ultrasound | Xa | | | | X | | | | X | |

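### The exacerbation count table has no observation window and the 48-week rate has no formula, although early termination leaves follow-up unequal

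*SAP*

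**What the plan says.** SAP 4.11.2 plans "The descriptive statistics of the 48-week pulmonary exacerbation rates based on different definitions" of exacerbation. It adds the number of subjects with 0, ≥1, ≥2 and ≥3 events, overall and by preceding Study 021 arm. SAP 4.1 attaches percentages and 95% confidence intervals to categorical summaries. Neither 4.11.2 nor the definitions in 5.6 give a numerator, a denominator or an observation window.

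On follow-up, Protocol 6.2.1 states that "treatment will comprise continuous daily treatment with ataluren for up to 96 weeks". SAP 2.1 records the termination: "strategic decision on March 2, 2017. All subject who are on-going by then will be discontinued".

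Three other places bear on the point:

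- SAP 6 removes the 48-week completer analysis, which Protocol 11.3 had planned for exacerbations among other endpoints.
- SAP 4.10.1 adjusts for exposure, per 100 patient-years, but only for treatment-emergent adverse events.
- Protocol 15.2, describing Study 009, explains the exacerbation rate as the number of events in 48 weeks.

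**The concern.** Subjects rolled over from Study 021 as they finished it, so their entry dates are spread out, but they all stop by one calendar date. Follow-up therefore differs by design. A table that classes subjects by number of events, with no window, gives a subject followed for half a year the same weight as one followed for a year and a half. The percentage with at least one event then reflects entry date as well as disease activity.

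The rate has a separate problem. Without a formula, two programmers could report different values for a listed secondary endpoint (SAP 2.3.2). What is at stake is whether the absolute exacerbation figures can be interpreted and compared with 48-week results, since Protocol 1 says the extension is meant to augment the double-blind efficacy data.

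**Working it through.** The documents state no follow-up range and no exacerbation rate, so there is no planned figure to reproduce. The range is derived and the event rate is assumed.

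**Inputs.** Protocol 1: "The first patient in study PTC124-021-CF initiated study drug treatment on 15 August 2014"; Study 021 "includes a treatment period of 48 weeks and an estimated recruitment period of 14 months". SAP 2.1: "Screening and baseline procedures are structured to avoid a gap in treatment between the double-blind study" and the extension, taken here as a gap of zero. Stop date: 2 March 2017.

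**Step 1, potential follow-up** = stop date − (Study 021 start + 48 weeks).

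- First entrant: 15 Aug 2014 + 48 weeks = 17 Jul 2015; to 2 Mar 2017 = 84.9 weeks.
- Last entrant at 14 months: 15 Oct 2015 + 48 weeks = 15 Sep 2016; to 2 Mar 2017 = 24.0 weeks.
- Lower end for other recruitment lengths: 32.7 weeks at 12 months, 15.3 at 16, 6.4 at 18. A 4-week gap shifts 24 to 85 down to about 20 to 81.

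On these dates nobody reaches 96 weeks.

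**Step 2, share unable to reach 48 weeks.** This needs a Study 021 start by 30 Apr 2015, which is 258 days after the first. With uniform accrual over 14 months (426 days), 1 − 258/426 = 39%. At 12 months (365 days) it is 29%; at 18 months (549 days) it is 53%. Dropout adds to these.

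**Step 3, effect on the table.** Let the true rate be λ per 48 weeks for everyone, and the mean at t weeks be m = λt/48. Then P(≥1) = 1 − exp(−m) for Poisson and 1 − 1/(1 + m) for negative binomial with k = 1. For λ = 1.5, m is 0.75, 1.5 and 2.65 at 24, 48 and 84.9 weeks. P(≥1) is then 53%, 78% and 93% (Poisson), or 43%, 60% and 73% (negative binomial).

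| λ per 48 weeks | P(≥1), Poisson, 24 vs 84.9 weeks | P(≥1), neg. binomial | P(≥3), Poisson |
|---|---|---|---|
| 0.5 | 22% vs 59% | 20% vs 47% | 0.2% vs 6% |
| 1.0 | 39% vs 83% | 33% vs 64% | 1.4% vs 26% |
| 1.5 | 53% vs 93% | 43% vs 73% | 4% vs 50% |
| 2.0 | 63% vs 97% | 50% vs 78% | 8% vs 69% |

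**Step 4, the pooled percentage.** Averaging the Poisson P(≥1) over uniform follow-up from a to b weeks gives 1 − [exp(−λa/48) − exp(−λb/48)] / [λ(b − a)/48]. For λ = 1.5, a = 24 and b = 84.9, this is 1 − (0.472 − 0.071)/1.902 = 79%, against 78% at a true 48 weeks. With 12 months of recruitment (a = 32.7) it is 82%; with 18 months (a = 6.4) it is 70%. The underlying rate is the same each time; only accrual changes.

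**Step 5, the rate under the two readings.**

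- Events counted within 48 weeks: 39% of subjects contribute on average (24 + 48)/2 = 36 of the 48 weeks. The expected count is 1 − 0.394 × (1 − 36/48) = 0.90 of the true value, about 10% too low before any dropout.
- Events over follow-up time, scaled to 48 weeks: with a constant rate, the expectation does not depend on follow-up.

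**The case against.** The plan is descriptive, has no hypothesis and tests nothing. A rate labelled 48-week, in a SAP dated July 2017 and so written after termination, can fairly be read as standardised to 48 weeks. Protocol 11.4.7.4 adjusted respiratory-event rates for exposure, which fits that reading, although it concerns a different endpoint whose summary SAP 6 removes. The follow-up range is derived from an estimated recruitment period. Expected Study 021 enrolment also moved from about 208 (Protocol 11.1) to about 279 (SAP 2.4), so the true recruitment length is uncertain. Step 4 shows that the pooled percentage with at least one event can fall close to the Week 48 value.

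Much of this stands. For the rate, the defect is a missing definition and not a demonstrated bias. The range is illustrative, although follow-up stays unequal at every recruitment length tried. The closeness in Step 4 arises because mean follow-up in that scenario, (24 + 84.9)/2 = 54 weeks, happens to lie near 48. It shifts with accrual and dropout, and the table would not reveal it.

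A reader might infer three stronger points that the documents do not support:

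- That the rate is a mean of subject-level rates, dominated by extreme values. SAP 4.11.2 does not say so, and very large values would need a very early dropout. At the 24-week administrative minimum one event scales to 2 per 48 weeks.
- That the results cannot be compared with Study 021 at all. A rate scaled to 48 weeks is on the same time scale, and the Study 021 analysis is not in these documents.
- That the comparison by preceding arm is biased. That requires follow-up to differ between arms, and randomisation in Study 021 should roughly balance entry dates.

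**Conclusion.** The concern holds for the count table. Followed as written, SAP 4.11.2 gives percentages that mix follow-up lengths differing about 3.5-fold (84.9/24.0). No completer analysis remains to provide a fixed window. The dependence on follow-up is large at every assumed rate from 0.5 to 2 per 48 weeks and under both distributions. For the rate, the finding is narrower: it is undefined, and one documented usage (Study 009) would make it about 10% too low in the 14-month scenario without dropout.

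The figures assume no transition gap, uniform accrual, follow-up to 2 March 2017 and a constant event rate common to all subjects (a common mean, in the negative binomial case). That follow-up is unequal needs only spread-out entry and a common stop date. The harm is mainly to overall and absolute figures on a secondary, descriptive endpoint. The change should be made, but it does not affect the primary safety objective.

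**What to change.** In SAP 4.11.2:

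1. Define the 48-week rate as total events divided by total follow-up in weeks, times 48. State when follow-up starts and ends. Report it overall and by preceding arm, with a 95% confidence interval that allows for over-dispersion, for example robust or bootstrap. A negative binomial model with log follow-up as offset is optional.
2. Replace or supplement the raw percentages with the Kaplan-Meier proportion of subjects with at least one event by Week 48, which handles censoring by the common stop date. Restricting the table to subjects followed for 48 weeks is less attractive, because it selects those who did not drop out and revives the completer analysis that SAP 6 removed.
3. If the 0, ≥1, ≥2, ≥3 counts are kept, show the distribution of follow-up time beside them.

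The cost is a small amount of programming and one extra interval in a descriptive SAP. No new data are needed.

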4.12. Tertiary Analyses

All tertiary analyses will be performed for the As-Treated population, unless specified otherwise.

4.12.1. Vital Signs

Vital sign parameters include systolic blood pressure (mmHg), diastolic blood pressure (mmHg), heart rate (bpm), pulse oximetry (%), and body temperature (°C). Vital sign assessments and the changes from baseline for each parameter will be summarized by visit. Maximal and minimal change from baseline in each parameter will also be summarized.

Weight gain and loss will be tabulated for the following categories: normal change from baseline, weight gain (5-<10%), weight gain (10-<20%) (Grade 2), weight gain (>=20%) (Grade 3), weight loss (5-<10%) (Grade 1), weight Loss (10-<20%) (Grade 2), and weight loss (>=20%) (Grade 3).

For adults (\geq 18 years of age), blood pressure parameters will be programmatically flagged for Stage 1 hypertension (systolic: \geq 140 to <160 mmHg, diastolic: \geq 90 to <100 mmHg), Stage 2 hypertension (systolic: \geq 160 mmHg, diastolic: \geq 100 mmHg), and hypotension (systolic: <90 mmHg, diastolic: <60 mmHg) [USDHHS 2003]. For children and adolescents (<18 years of age), blood pressure parameters will be programmatically evaluated based upon height- and age-specific nomograms, and categorized by percentile (<95%, \geq 95% to <99%, and \geq 99%) [USDHHS 2005]. A summary of the number and percent of subjects by systolic and diastolic blood pressure categories of <95%, \geq 95% to <99%, and \geq 99% as defined as follows.

<95%: for age <18 years old, SBP <95% and DBP <95%; for age \geq 18 years old, SBP <140 mmHg and DBP <90 mmHg.

 \geq 95% to <99%: for age <18 years old, SBP \geq 95% to <99% or DBP \geq 95% to <99%; for age \geq 18 years old, SBP \geq 140 to <160 mmHg or DBP \geq 90 to <100 mmHg. In addition, none of SBP and DBP meets the following criteria of \geq 99%.

 \geq 99%: for age \leq 18 years old, SBP \geq 99% or DBP \geq 99%; for age \geq 18 years old, SBP \geq 160 mmHg or DBP \geq 100 mmHg.

Shift tables will be presented showing change in results from baseline using above <95%, $\ge95\%$ to <99%, and $\ge99\%$ categories.

As necessary, vital signs will be described by duration of study drug exposure, by dose, by age group, by sex, by race, by weight, and for special populations (eg, antibiotic use).

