11.4.6. Secondary Variables

11.4.6.1 Spirometry

Both absolute change and relative change in %-predicted FEV_1 from Baseline at each visit will be summarized descriptively. Pediatric equations for calculating %-predicted FEV_1 [Wang 1993] will be used from 6 to <16 years of age for female subjects and from 6 to <18 years of age for male subjects. For males or females >18 years of age, an adult equation for calculating %-predicted FEV_1 [Hankinson 1999] will be used. Each %-predicted FEV_1 will be based on the height value obtained at the same study visit. The changes from baseline to each post-baseline visit will be analyzed using paired t-tests.

Above analyses will be repeated for FVC and FEF₂₅₋₇₅.

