4.12.2. Body Weight, Height, and BMI

Descriptive statistics on change from baseline in the body weight (kg), height (cm), and BMI will be displayed at each visit.

The change in weight or height percentiles calculated by using Centers for Disease Control and Prevention (CDC) growth chart [CDC] will be analyzed similarly for subjects < 18 years old at baseline.

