5.1. Baseline

In general, Baseline is defined as the last non-missing valid assessment prior to or on the date of the first dose. The assessment at week 48 in study 021 will be used as the baseline if corresponding baseline in study 021e is missing.

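### The weight-gain grades in SAP 4.12.1 have no age limit, so ordinary growth in subjects under 18 can be tabulated as Grade 2 and occasionally Grade 3 weight gain

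*SAP*

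**What the plan says.** SAP 4.12.1 introduces the table with "Weight gain and loss will be tabulated for the following categories: normal change from baseline" and then lists the bands. On the gain side, the 5% to under 10% band carries no grade, followed by "weight gain (10-<20%) (Grade 2" and "weight gain (>=20%) (Grade 3". On the loss side, the three bands with the same cut-points are Grades 1, 2 and 3. The normal-change category has no numeric range.

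The population is set in SAP 4.12: "All tertiary analyses will be performed for the As-Treated population, unless specified otherwise". Nothing in the weight table specifies otherwise. The reference value is fixed by SAP 5.1: "Baseline is defined as the last non-missing valid assessment prior to or on the date of the first dose".

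Children belong to this population. Protocol 11.4.6.1 says the pediatric FEV1 equations "will be used from 6 to <16 years of age for female subjects and from 6 to <18 years of age for male subjects". SAP 4.6 has a baseline age category of under 18, and Protocol 14.1.2 expects many enrolled patients to be sexually immature.

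Two neighbouring provisions do allow for growth. SAP 4.12.1 evaluates blood pressure in under-18s against height- and age-specific nomograms. SAP 4.12.2 summarises change in CDC weight and height percentiles "for subjects < 18 years old at baseline". SAP 4.12.1 also permits vital signs to be described by age group where needed, without requiring it.

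**The concern.** Percent change from a fixed baseline is a reasonable measure of weight gain in adults. In a growing child it mixes growth with anything the drug may do, and the mixture drifts upward with follow-up. The SAP recognises this for blood pressure and for the CDC summary, but not for the graded weight bands.

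The labels matter because the same grade numbers have a defined meaning elsewhere. SAP 4.10.1 equates Grade 3 with severe, and Protocol 6.3.1 says severe abnormalities should generally be considered clinically significant. The study is open-label and every subject receives ataluren, so no concurrent untreated group would show the same growth-driven counts off drug. A reader of the safety report could take them for a weight signal.

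There is a smaller problem in the other direction. If normal change means neither a gain nor a loss of 5% or more, a child whose weight does not move for a year or longer is counted as normal.

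**Working it through.** The plan gives no figure on this point, so there is nothing to reproduce. The check asks how fast a child must grow to enter each grade, and how long children could have been followed.

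**Inputs from the documents**
- Grade 2 gain from 10%, Grade 3 gain from 20%, fixed baseline (SAP 4.12.1, 5.1).
- First parent-study dose on 15 August 2014, 48 weeks of parent-study treatment, planned recruitment of 14 months (Protocol 1).
- Termination on 2 March 2017, with ongoing subjects discontinued (SAP 2.1).

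**Assumption, not in the documents:** ordinary growth of 5-15% of baseline weight a year, taken as linear. A 40 kg child gaining 2 kg a year is at 5%; a 20 kg child gaining 3 kg a year is at 15%.

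**Step 1. Longest possible exposure, assuming no gap between studies**
- Earliest entrant: 15 August 2014 + 48 weeks = 17 July 2015. To 2 March 2017 is 594 days, and 594/7 = 84.9, about 85 weeks.
- Last planned entrant: 14 months later, 15 September 2016. To 2 March 2017 is 168 days, or 24 weeks.
- Midpoint of the two: about 54 weeks.

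**Step 2. Percent gain = annual rate × weeks/52**

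| Annual rate | Week 24 | Week 48 | Week 54 | Week 85 |
|---|---|---|---|---|
| 5% | 2.3 | 4.6 | 5.2 | 8.2 |
| 10% | 4.6 | 9.2 | 10.4 | 16.3 |
| 15% | 6.9 | 13.8 | 15.6 | 24.5 |

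Across the assumed range, gain is about 5-14% at Week 48 and 8-25% at Week 85.

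**Step 3. Annual rate needed = threshold × 52/weeks**

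| Exposure | Grade 2 (10%) | Grade 3 (20%) |
|---|---|---|
| 24 weeks | 21.7% | 43.3% |
| 48 weeks | 10.8% | 21.7% |
| 54 weeks | 9.6% | 19.3% |
| 85 weeks | 6.1% | 12.2% |

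Compound growth changes little: at 84 weeks it gives 6.1% and 12.0% a year.

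**Step 4. Time to reach a grade = threshold/rate × 52**
- Grade 2: about 35 weeks at 15% a year, 52 weeks at 10%, 104 weeks at 5%. The slowest growers in the range never reach it, even over the planned 96 weeks.
- Grade 3: about 69 weeks at 15% a year. Within the assumed range nobody reaches it sooner, so it is confined to entrants with at least 69 of the possible 85 weeks.

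**Step 5. The normal-change category.** By exclusion from the other bands it runs from above -5% to below +5%. A child with 0% change falls there at every visit. So does a child growing at up to about 3% a year at Week 85 (5 × 52/85 = 3.1%).

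**The case against.** The case for leaving the table alone is substantial. It is tertiary, and SAP 4.2 calls all analyses in the study descriptive. Adverse event severity is graded by the investigator (SAP 4.10.1), and nothing in the SAP feeds these programmed bands into adverse event counts. By-subject listings are planned (SAP 4.1), and an age-group description is permitted. All of this stands and keeps the point minor. It does not correct the table: splitting it by age would leave the same grades on the children.

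Four stronger readings are tempting, and the documents do not support them.

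- **Most children will be graded, many at Grade 3.** The documents give neither a growth rate nor the share of subjects under 18. A slow grower at 5% a year never reaches Grade 2, and at 24 weeks of exposure nobody in the assumed range does. Termination in March 2017 cuts off most of the follow-up that Grade 3 would need.
- **Poor growth is hidden.** The CDC percentile summary in SAP 4.12.2 would show flat weight in under-18s as a falling percentile. The range of the normal-change category is also inferred, not stated.
- **The table contradicts a protocol statement that weight gain is favourable.** Protocol 14.4.4 treats weight and BMI as nonspecific outcomes of general well-being. It says CF patients are usually underweight, but does not declare weight gain a benefit.
- **All percent-change bands should be limited to adults.** Growth does not inflate the loss bands. A child who loses weight is a case where they are informative.

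**Conclusion.** The defect holds as a minor one. Followed as written, SAP 4.12.1 can label ordinary growth as graded weight gain because the gain bands have no age restriction and the baseline is fixed. Under assumed growth of 5-15% a year, Grade 2 is reachable for many growing children with about a year or more of exposure. Grade 3 is limited to faster growers, above about 12% a year, among the earliest entrants. The CDC summary limits the harm but does not change the labels.

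The size rests on three assumptions: the growth range, linear growth, and 2 March 2017 as the end of treatment with no gap after the parent study. How many subjects are affected cannot be derived from the documents. The primary adverse event and laboratory analyses are not touched.

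**What to change.** Amend SAP 4.12.1 before database lock, as the SAP overview allows:

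1. Apply the weight-gain grades only to subjects aged 18 or over at baseline.
2. Keep the weight-loss bands for all ages.
3. For subjects under 18 at baseline, replace the gain grades with categories of change in CDC weight-for-age percentile, or in z-score from the same reference. Z-score is preferable to counting crossings of fixed percentiles: it also captures a fall within a band (for example 49th to 26th) or one that starts below the 5th percentile, which matters in a population that Protocol 14.4.4 describes as usually underweight.
4. Give the normal-change category a numeric range.

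The cost is one table split by age. Weight and height are already collected at every visit and the percentiles are already planned, so no new data are needed.
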